# 8.10.5 Discontinued Participants Continuing to be Monitored in the Study

At any point if a participant discontinues from treatment but continues to be monitored in the study, a subset of study procedures specified in the SoA may be completed at the discretion

of the investigator and with Sponsor agreement. The subset of study procedures completed will be communicated in a PCL.

# 8.10.6 Poststudy (Visit10)

Participants will be required to return to clinic approximately 14 days after the last dose of study intervention for the poststudy visit. If the poststudy visit occurs less than 14 days after the last dose of study intervention, a subsequent follow-up telephone call should be made at 14 days post the last dose of study intervention to determine if any AEs have occurred since the poststudy clinic visit.

## 8.10.7 Study Design/Dosing/Procedures Modifications Permitted Within Protocol Parameters

See Section 6.6 for Dosing modifications permitted per protocol.

This is a Phase 1 assessment of MK-8189 in humans, and the PK, pharmacodynamic, and safety profiles of the compound are still being elucidated. This protocol is written with some flexibility to accommodate the inherent dynamic nature of Phase 1 clinical studies. Modifications to the dose, dosing regimen, and/or clinical or laboratory procedures currently outlined may be required to achieve the scientific goals of the study objectives and/or to ensure appropriate safety monitoring of the study participants.

As such, some alterations from the currently outlined dose and/or dosing regimen may be permitted based on newly available data, but the maximum daily dose may not exceed those currently outlined in the protocol.

- Repeat of or decrease in the dose and/or titration steps of the study intervention administered.
- Decrease in the duration of study intervention administration (e.g., number of days).
- Addition of PK pause.
- Instructions to take study intervention with or without food or drink may also be modified based on newly available data.
- Modification of the PK sample processing and shipping details based on newly available data.

The PK sampling scheme currently outlined in the protocol may be modified during the study based on newly available PK or pharmacodynamic data (e.g., to obtain data closer to the time of peak plasma concentrations). If indicated, these collected samples may also be assayed in an exploratory manner for metabolites and/or additional pharmacodynamic markers.

Up to an additional 50 mL of blood may be drawn for safety, PK, and/or pharmacodynamic analyses. The total blood volume withdrawn from any single participant will not exceed the maximum allowable volume during his/her participation in the entire study (Appendix 8).

The timing of procedures for assessment of safety procedures (e.g., vital signs, ECG, safety laboratory tests, etc.) may be modified during the study based on newly available data. Additional laboratory safety tests may be added to blood samples previously drawn to obtain additional safety information. These changes will not increase the number of study procedures for a given participant during his/her participation in the entire study.

It is understood that the current study may use some or none of the alterations described above. Any alteration made to this protocol to meet the study objectives must be detailed by the Sponsor in a letter to the Study File and forwarded to the investigator for retention. The letter may be forwarded to the IRB/IEC at the discretion of the investigator.

#### 9 STATISTICAL ANALYSIS PLAN

#### 9.1 Statistical Analysis Plan Summary

This section contains a brief summary of the statistical analyses for this trial. Full detail is in the Statistical Analysis Plan (SAP) (Section 9.2).

#### Safety:

For the primary objective, all AEs and AEs leading to discontinuation of study intervention will be summarized and tabulated.

Summary statistics and plots will be generated for raw laboratory safety tests, 12-lead ECGs, and/or VS as well as for change from baseline, as deemed clinically appropriate. Depending on the safety parameter, the difference from baseline will either be computed on the original scale (raw change from baseline) or on the log scale and back transformed for reporting (percent change from baseline).

For exploratory objectives, summary statistics and plots will be generated for Barnes Akathisia Rating Scale (BARS), Abnormal Involuntary Movement Scale (AIMS) and Simpson Angus Scale (SAS), as well as for change from baseline. Responses to the C-SSRS will be listed. Additionally, summary statistics for change from baseline will be provided for MMSE-2, and NPI.

#### Pharmacokinetics:

Descriptive summary statistics will also be provided for MK-8189 C24hr.

#### 9.2 **Responsibility for Analyses**

The statistical analysis of the data obtained from this study will be conducted by, or under the direct auspices of, the Early Clinical Development Statistics Department in collaboration with the Quantitative Pharmacology and Pharmacometrics Department and Translational Pharmacology Department of the Sponsor. If, after the study has begun, changes are made to the statistical analysis plan stated below, then these deviations to the plan will be listed, along with an explanation as to why they occurred, in the Clinical Study Report.

## 9.3 Hypotheses/Estimation

#### **Objectives:**

Refer to Section 3 for primary and exploratory objectives.

## 9.4 Analysis Endpoints

Safety: Primary safety endpoints will include all types of AEs and AEs leading to discontinuation of study intervention.

Additionally, for exploratory purposes, laboratory safety tests, 12-lead ECGs, and VS will be summarized. For laboratory safety tests, baseline is defined as readings obtained prior to first dose (Note: Readings from screening (Visit 1) will not serve as baseline for these parameters). For 12-lead ECGs and VS, baseline is defined as Day 1 predose readings.

## Exploratory:

BARS, AIMS, and SAS for all participants.

The Columbia Suicide Severity Rating Scale (C-SSRS) will be used to systematically and prospectively ascertain and document the occurrence of suicidal events (i.e., ideation and behavior). Responses on the C-SSRS are classified according to 11 prespecified categories as described in procedure manual. The most severe treatment-emergent ideation and behavior event reported at a visit will be used for analysis and reporting. An event is considered treatment-emergent during the assessment phase if it newly emerged or is more severe compared to recent history (i.e., protocol-defined recent history prior to entering the trial as stated in the Inclusion/Exclusion criteria for suicidal ideation/behavior, up to and including the randomization visit). Readings from Day -5 to Day-3 in Visit 2 will serve as baseline.

MMSE-2, and NPI for all participants. Readings from screening (Visit 1) will serve as baseline. (Note: For NPI, if AP is washed off, the NPI readings obtained post washout will be used as baseline.)

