#### Figure 1 Study Schema

### **1.3** Schedule of Activities

	Screening	Baseline	Intervention							Poststudy a	
Visit	1	2	3	4	5	6	7	8	9 	10	
Scheduled Visit Day plus Window	Up to -42	-5 to -3	1	4	7	10 j	14 ±1	21 ±1	28 +1	LD+14+2	
Administrative Procedures											
Informed Consent – Study Participant	X										Section 8.1.1.1
Informed Consent – Trial Partner	Х										Section 8.1.1.1
Informed Consent for FBR	Х										Section 8.1.1.2
Participant ID Card	Х										Section 8.1.3
Inclusion/Exclusion Criteria	Х	х									Section 5.1 & Section 5.2 Specific criteria may be reviewed before randomization
Medical History (includes psychiatric history and substance usage)	Х										Substances: Drugs, alcohol, tobacco, and caffeine Section 8.10.2
Prior/Concomitant Medication Review	X									X	Section 6.5, Section 8.10.2
Assignment of Treatment/Randomization Number			Х								
Study Intervention Administration b			X						X		The last dose will be on Day 28 regardless of the Study Day Visit 9 falls on.
Study Intervention Dispensing/Review			X	Х	Х	X	X	X	X		Collect prior medication bottle before dispensing new one.
Study Intervention Diary Dispensing/Review			Х	Х	Х	X	X	X	Х		Review diary upon participants return to the CRU.
Daily Phone Call c			XX								
Optional Domiciling	omiciling X								X		See Section 8.1.12
Safety Procedures	Safety Procedures										
Full physical examination	X	Х				 				Х	
Height	Х										

	Screening	Baseline	Intervention						Poststudy a		
Visit	1	2	3	4	5	6	7	8	9 	10	
Scheduled Visit Day plus											
Window	Up to -42	-5 to -3	1	4	7	10 j	14 ±1	21 ±1	28 +1	LD+14+2	
Weight	Х	Х								Х	BMI to be calculated only at Screening
Full Neurological Exam	Х	Х									Section 10.10
Targeted Neurological Exam d					Х		Х	Х	Х	Х	Section 10.10
Vital Signs (pulse rate, blood pressure) e, f	Х		Х	Х	Х	Х	X	X	X	Х	Section 8.3.2.1
Orthostatic Vital Signs (pulse rate, blood pressure) e	Х		Х	Х	Х	Х	х	х	х	х	Section 8.3.2.2
Vital Signs (respiratory rate, body temperature) e	Х		Х		Х		Х	х	х	Х	Section 8.3.2.1
12-lead ECG e, f	Х		Х		Х		Х	Х	Х	Х	Section 8.3.3
Serum hCG Pregnancy Test (as needed in WOCBP only)	Х										Section 5.1 & Section 8.3.5
Urine hCG Pregnancy Test (as needed in WOCBP Only)		Х			Х		X	X	X	Х	Section 5.1 & Section 8.3.5

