Serum FSH (as need in WONCBP only)	Х										
HIV, Hepatitis B and C Screen (per site SOP)	Х										
UDS/BDS (per site SOP)	Х	Х									
Laboratory Safety Tests (hematology, chemistry, urinalysis) g	Х	Х			Х		x	x	x	X	Section 10.2
Columbia Suicide Severity Rating Scale (C-SSRS) – Baseline Version	Х										Section 8.3.6.1
Columbia Suicide Severity Rating Scale (C-SSRS) – Since Last Assessment Version d		Х	X	Х	Х	х	х	х	x	Х	Section 8.3.6.1
Neuropsychiatric Inventory (NPI) d, h	Х								X		Section 8.3.10 & Section 8.10.2
Mini Mental State Examination (MMSE-2) d	X								X		Section 8.3.9

	Screening	Baseline	Intervention Posts							Poststudy a	
Visit	1	2	3	4	5	6	7	8	9 	10	
Scheduled Visit Day plus											
Window	Up to -42	-5 to -3	1	4	7	10 j	14 ±1	21 ±1	28 +1	LD+14+2	
Rosen-Modified Hachinski Ischemic Score (MHIS)	Х										Section 8.3.8
Barnes Akathisia Rating Scale (BARS) d, i		Х			Х		Х	х	Х	$\mathbf{X}^{\mathrm{i}}$	Section 8.3.11
Abnormal Involuntary Movement Scale (AIMS) d, i		Х			Х		X	х	X	$\mathbf{X}^{\mathrm{i}}$	Section 8.3.11
Simpson Angus Scale (SAS) d, i		Х			Х		Х	Х	Х	X i	Section 8.3.11
AE/SAE review	X									X	
Pharmacokinetics											
Blood for Plasma MK-8189 and/or Metabolites Assay			х		X		х	X	х		On days noted, 2 blood samples will be collected: 1) prior to dosing (fasted) 2) 2-4 hours post dose Note: If Visit 9 occurs on Day 29, , only 1 blood sample will be collected as there will be no dose on this day.
Blood for Plasma Donepezil Assay k			Х		Х		X	Х	X		Blood collected prior to dosing (fasted).
Blood for Plasma Memantine Assay k			Х		Х		X	Х	Х		Blood collected prior to dosing (fasted)
Biomarkers											
Blood for Exploratory Plasma Biomarkers for AD Diagnosis			Х								See Section 8.8.2
Blood for Genetic Analysis m			Х								Collect predose from enrolled participants only.

		Screening	Baseline		Intervention Poststudy a							
	Visit	1	2	3	4	5	6	7	8	9 	10	
	Scheduled Visit Day plus											
	Window	Up to -42	-5 to -3	1	4	7	10 j	14 ±1	21 ±1	28 +1	LD+14+2	
AE	=adverse event; BDS=blood drug	screen; C-SSR	S=Columbia	-Suici	de Seve	erity Ra	ting Sca	ale; DN	A=deox	xyribon	ucleic acid; E	CG=electrocardiogram; FBR=future biomedical

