res	earch; FSH=follicle stimulating ho	rmone; hCG=h	uman choric	onic go	nadotr	opin; II	)=ident	ification	n; SAE=	=seriou	s adverse even	t; SOP=standard operating procedure;
UD	S=urine drug screen; VS=vital sig	ns; WOCBP=v	vomen of chi	ildbea	ing po	tential;	WONC	BP=wo	men of	nonchi	Idbearing pote	ential
a.	Poststudy visit procedures sho	build also be p	ertormed to	or par	ticipar	its who	disco	ntinue	d early	from s	study interver	ntion.
b.	QD dosing at approximately t	he same time	each morn	ıng (l	Days 1	-28) en	ther in	the CF	CU  or a	it home	e. During sch	eduled CRU visits, participants should be
	administered study intervention	on fasted in th	ne CRU. At	hom	e study	interv	ention	admin	istratic	on will	be with or w	ithout food and will be recorded in study
	intervention diary by the parti	cipant/trial p	artner. Part	icipan	ts will	be sup	ervise	d for a	t least (	6 hours	s following th	ne first administration of study intervention
	and following the first admini	stration of ea	ch study in	tervei	ition ti	tration	(see S	ection	8.1.8).			
c.	While participants are outpati	ent, site staff	will call pa	rticip	ants da	ally to	check s	study a	dminis	stration	i compliance,	, review AEs, and remind participants of
	their next scheduled visit (if a	pplicable).	1 10									
d.	Collected after dosing and an	optional light	t breakfast	on stu	idy trea	atment	admin	istratic	on days	5.		
e.	Collected prior to dosing on s	tudy treatmen	nt administi	ation	days.		 					
t.	Vital sign measurements at So	creening will	be taken in	tripli	cate. L	Day I E	CGs a	nd vita	l sign i	measur	rements will	be taken in triplicate within 3 hours prior to
	dosing. Single ECGs and vita	l sign measur	ements will	l be c	ollecte	d on al	l other	days.				
g.	Safety laboratory Baseline res	sults will be r	eviewed pr	or to	Day I	dosing	, All s	afety la	aborate	ory col	lection will b	e fasted and prior to dosing on study
	treatment administration days											
h.	For participants that must was	shout of prior	antipsycho	tic tre	eatmen	it at Sci	reening	g, the N	NPI 1s t	to be re	epeated prior	to randomization after a minimum 2-week
1.	washout or 5 half-lives, which	never is longe	er.	1	1		. .					
1.	Poststudy assessment required	d only if clini	cally mean	ingful	chang	ges on I	Day 28	•				
J.	Visit 6 (Day 10) will only occ	cur for Litration	on 3.	1.	1	••	. /					

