#### **Medical Conditions**

- 1. Has agitation/aggression or psychosis that is attributable to concomitant medications, environmental conditions, substance abuse, or an active medical or psychiatric condition.
- 2. Has a MHIS Score > 4 at Screening (i.e., evidence of vascular dementia).
- 3. Has a known history of stroke or evidence from prior MRI scan (if available) that is clinically important in the investigator's opinion.
- 4. Has evidence of a clinically relevant neurological disorder other than the disease being studied (i.e., probable AD) at Screening, including but not limited to: vascular dementia, parkinsonism, frontotemporal dementia, Huntington's disease, amyotrophic lateral sclerosis, multiple sclerosis, progressive supranuclear palsy, neurosyphilis, dementia with Lewy bodies, posterior cortical atrophy, logopenic primary progressive aphasia, other types of dementia, intellectual disability, hypoxic cerebral damage, cognitive impairment due to other disorders, or head trauma with loss of consciousness that led to persistent cognitive deficits.
- 5. Has a history of seizures or epilepsy within the last 5 years before Screening.
- 6. Has evidence of a clinically relevant or unstable psychiatric disorder, based on DSM-5 criteria, including schizophrenia, schizophrenia spectrum or other psychotic disorder, bipolar disorder, major depressive disorder, or delirium. Note: Major depressive disorder in remission is not exclusionary and mild, stable, treated depression is not exclusionary.
- 7. Is at imminent risk of self-harm, based on clinical interview or on the C-SSRS, or of harm to others in the opinion of the investigator. Participants must be excluded if they report suicidal ideation with intent, with or without a plan (i.e., suicidal ideation Item 4 or 5 on the C-SSRS) in the past 2 months or suicidal behavior in the past 6 months.
- 8. Has a history of alcoholism or drug dependency/abuse within the last 5 years before screening.

MK-8189-017-04 FINAL PROTOCOL

39

9. Has a history of cancer (malignancy).

Exceptions: (1) Adequately treated nonmelanomatous skin carcinoma or carcinoma in situ of the cervix or; (2) Other malignancies that have been successfully treated with appropriate follow up and therefore unlikely to recur for the duration of the study, in the opinion of the investigator and with agreement of the Sponsor (e.g., malignancies that have been successfully treated  $\geq 10$  years prior to the prestudy [screening] visit).

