#### 8.3.7 Rater Expectations and Training for Clinical and Cognitive Assessments

For this study, potential raters of clinical and/or cognitive assessments (BARS [Section 8.3.11], SAS [Section 8.3.11], AIMS [Section 8.3.11], C-SSRS [8.3.6.1], MHIS [Section 8.3.8], MMSE-2 [Section 8.3.9], and NPI [Section 8.3.10]) will be identified based on review of their reported credentials against target minimum credentials for education, prior experience with AD, MCI or similar populations and direct, hands-on experience with study-specific or similar assessments. Persons whose credentials meet or exceed those targets will then be considered 'qualified' as raters in this trial. For the MMSE-2 and NPI, raters will subsequently complete overview, didactic, protocol-specific training before conducting

assessments in this trial. It is recommended that the same rater conducts the same assessments throughout the study for a given participant, where feasible.

All clinical and cognitive assessments will be administered after dosing and following an optional light breakfast provided by the CRU.

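### The C-SSRS treatment-emergent rule in Section 9.4 counts the Day 1 post-dose interview as pre-treatment history

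*Combined protocol and SAP*

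**What the plan says.** Under the Exploratory part of Section 9.4, a C-SSRS event is treatment-emergent if it is new or more severe than "recent history prior to entering the trial as stated in the Inclusion/Exclusion criteria for suicidal ideation/behavior, up to and including the randomization visit". The worst treatment-emergent event at each visit is what goes forward to analysis and reporting.

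The eligibility look-back that this refers to is Exclusion 7 in Section 5.2. It bars ideation at items 4 or 5 "in the past 2 months or suicidal behavior in the past 6 months".

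The same Section 9.4 paragraph closes with "Readings from Day -5 to Day-3 in Visit 2 will serve as baseline". It does not say whether that sentence governs the treatment-emergent flag.

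In the Schedule of Activities (Section 1.3), the row "Assignment of Treatment/Randomization Number" is marked only at Visit 3, Day 1. The C-SSRS at that visit is the "Since Last Assessment Version" and carries footnote d, which places it after dosing on treatment days. Section 8.3.7 names the C-SSRS among its scales and says: "All clinical and cognitive assessments will be administered after dosing and following an optional light breakfast provided by the CRU".

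**The concern.** A treatment-emergent flag should compare what happens after the first dose with what was present before it. Here the stated end of the reference window is a visit whose only scheduled C-SSRS follows the first dose, so the first on-treatment reading sits on the history side.

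Elsewhere Section 9.4 keeps the two sides apart: the laboratory baseline ends before the first dose, and the ECG and vital-sign baselines are Day 1 predose readings. Only the C-SSRS window has no predose limit.

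At stake is the classification of suicidality for a CNS-active drug. An event that starts after the first dose and is reported on Day 1 would not be flagged. A later event that exceeds the true predose history, but not the Day 1 level, would also be missed.

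**Working it through.** **Order of events**

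| Step | Timing | Source |
|---|---|---|
| C-SSRS, Baseline version | Visit 1 | Section 1.3 |
| C-SSRS, last scheduled before dosing | Visit 2, Day -5 to -3 | Sections 1.3, 8.10.3 |
| Randomization and first dose | Visit 3, Day 1 | Sections 1.3, 8.10.4 |
| C-SSRS at Visit 3 | Day 1, after dosing | Section 1.3 footnote d; Section 8.3.7 |
| Later C-SSRS | Days 4, 7, 14, 21, 28 and poststudy; Day 10 under Titration 3 only | Section 1.3 |

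After Day 1 there are therefore 6 scheduled assessments under Titration 1 or 2, and 7 under Titration 3. Including Day 1, 1 of 7 (or 1 of 8) post-dose assessments falls inside the history window.

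**The two rules compared, for ideation**

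Let *h* be the worst ideation level in the look-back through Visit 2, *b* the level reported post-dose on Day 1, and *c* the level at a later visit. Exclusion 7 bars items 4 and 5, so *h* runs from 0 to 3 in an eligible participant; *b* and *c* run from 0 to 5. Assume that anything reported on Day 1 above *h* began after the dose.

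- Written rule: the reference is max(*h*, *b*). Day 1 is never flagged. A later visit is flagged if *c* > max(*h*, *b*).
- Predose rule: the reference is *h*. Day 1 is flagged if *b* > *h*, and a later visit if *c* > *h*.

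The rules differ:

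- on Day 1 when *b* > *h*: for *h* = 0, 1, 2, 3 this gives 5 + 4 + 3 + 2 = 14 of the 4 × 6 = 24 pairs;
- at a later visit when *h* < *c* ≤ *b*: 15 + 10 + 6 + 3 = 34 of the 4 × 6 × 6 = 144 triples.

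These count possible combinations and are not probabilities. They show the direction: in every differing case the written rule drops a flag, and in none does it add one.

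**Example.** No ideation through Visit 2 (*h* = 0), level 2 beginning after the dose on Day 1 (*b* = 2), level 2 on Day 4 (*c* = 2). Written rule: the reference is 2, so neither visit is flagged. Predose rule: 2 > 0, so both are flagged.

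**Does the Visit 2 sentence settle it?** Take level 2 at Screening within the look-back, 0 at Visit 2, and 2 on Day 14. Against the recent-history window, 2 > 2 is false and nothing is flagged. Against Visit 2 alone, 2 > 0 is true and Day 14 is flagged. The two sentences are different rules, and the plan does not say which prevails.

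The scope of the Visit 2 sentence is also open. The block begins with "BARS, AIMS, and SAS for all participants"; these scales are collected at Visit 2, have change-from-baseline summaries in Section 9.6, and are given no other baseline in Section 9.4.

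**The case against.** The strongest reply is that predose intent is visible: the definition speaks of history before trial entry, and the paragraph ends by naming Visit 2 as baseline. That may well be the intent. But the same parenthesis gives an explicit end point, which a programmer would apply, and the Visit 2 sentence yields different flags.

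Second, Section 9.6 specifies only a listing of C-SSRS responses. Each Day 1 response stays visible, all adverse events are reported from randomization (Section 8.4.1), and suicidal adverse events are recorded as events of clinical interest (Section 8.3.6.1). This stands and limits the harm to classification; no event is lost. The flag still has a role, because Section 9.4 says treatment-emergent events are used for analysis and reporting.

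Third, the Day 1 form covers the 3 to 5 days since Visit 2 as well as the hours after dosing, so most of its recall period is predose. With a median Tmax of 10 to 24 hours (Section 2.2.2), the interview may also precede peak exposure. Moving the whole form to the on-treatment side would create the opposite error. This stands too, and is why onset has to be recorded.

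Fourth, the combination counts overstate later masking. Of the 34 triples, 24 have a Day 1 level of 4 or 5 (10 at level 4, 14 at level 5). Section 8.3.6.1 requires same-day evaluation of such participants, and many would not continue to later visits. That leaves 10 triples with *b* of 3 or less. The Day 1 flag itself is lost whether or not the participant continues.

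**Conclusion.** The concern holds. As written, the reference window contains a post-dose reading, and following it can only suppress treatment-emergent flags.

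It affects one Day 1 reading per participant, in up to about 28 participants (21 on MK-8189, 7 on placebo), and carries that level into 6 or 7 later comparisons. Flags change only if the Day 1 level exceeds the predose history, or a later level exceeds that history without exceeding the Day 1 level. The documents give no C-SSRS event rate, so the number affected cannot be estimated and may be zero.

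The impact is minor, and the primary adverse-event endpoint and event capture are unaffected. The wording should still be corrected, because the error runs in one direction on a suicidality measure and is cheap to remove. The conclusion rests on the scheduled order of assessments, with no unscheduled predose C-SSRS on Day 1.

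**What to change.** In Section 9.4:

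- End the recent-history window before the first dose: the Exclusion 7 look-back (2 months for ideation, 6 months for behavior) through the last C-SSRS before the first dose, at Visit 2.
- Treat the Day 1 post-dose C-SSRS as on-treatment unless onset is documented as before the dose, and flag events of uncertain onset.
- State that this window, not the Visit 2 reading alone, governs the flag, and say which scales the Visit 2 baseline sentence covers.

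The cost is one phrase and one clarifying sentence, plus a small data-collection addition: an onset entry (before, after or uncertain relative to the first dose) for any event reported at the Day 1 C-SSRS. No visit or interview is added. The drawback is that recall of onset is imperfect in participants with MMSE-2 scores of 10 to 24, so flagging uncertain onset may count some events that began in the 3 to 5 days between Visit 2 and the first dose.
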